4.2 Number of Patients

Based on the optimal Simon's two-stage design, at least 3 responders among stage 1 patients (N=10) are required to enter into a stage 2. The stage 2 will be delayed until the completion of ≥ 4 cycles of study medication in the last patient in stage 1, so-called interim analysis of stage 1. A total of 25 patients with EBV- and CD30-positive lymphomas will be enrolled.

4.3 Duration of Study

This study will last approximately 30 months to reach the final analyses of the ORR and PFS (24 months of enrollment plus 6 months of additional follow-up after the last patient-in).

5 STUDY POPULATION

5.1 Inclusion Criteria

Each patient must meet all of the following inclusion criteria to be enrolled in the study:

1. Male or female patients 18 years or older
2. Patients with relapsed or refractory EBV- and CD30-positive lymphomas
 - a. EBV-positivity determined by EBV *in situ* hybridization at participating centers
 - i. Extranodal NK/T-cell lymphoma, nasal type
 - ii. EBV-positive peripheral T-cell lymphoma, not otherwise specified
 - iii. EBV-positive diffuse large B-cell lymphoma of the elderly
 - iv. Plasmablastic lymphoma
 - v. Lymphomatoid granulomatosis
 - vi. Hydroa vacciniforme-like T-cell lymphoma
 - vii. Other EBV-positive lymphoproliferative disorders
 - b. CD30-positivity determined by a specialized hemato-pathologist. CD30 positivity defined as 10% or greater tumor cells expressing CD30 at any intensity greater than or equal to 1+ with any cellular distribution pattern.
 - c. Relapsed or refractory disease that fails to at least one and maximum four regimens including anthracycline-based chemotherapy; if anthracycline-based regimen is not standard treatment of certain subtypes (e.g. hydroa vacciniforme-like T-cell lymphoma or EBV-positive lymphoproliferative disorder, etc), a prior chemotherapy is acceptable.
3. ECOG Performance status 0-2
4. At least one measurable lesion based on revised Cheson's or modified SWAT criteria
5. Provision archival tumor tissues (4 μ m thickness x 5 unstained slides) and blood samples
6. Adequate hematologic function: absolute neutrophil count (ANC) \geq 1,500/ μ L, platelet count \geq 75,000/ μ L, and hemoglobin \geq 8.0 g/dL unless there is known hematologic tumor marrow involvement (ANC \geq 1,000/ μ L and platelet count \geq 50,000/ μ L if there is known bone marrow involvement)
7. Adequate liver function: total bilirubin $<$ 1.5 x the upper limit of the normal (ULN) unless the elevation is known to be due to Gilbert syndrome and ALT or AST $<$ 3 x ULN (AST and AST $<$ 5 x ULN if their elevation can be reasonably ascribed to the presence of hematologic tumor in liver)
8. Adequate renal function: serum creatinine $<$ 2.0 mg/dL and/or creatinine clearance or calculated creatinine clearance $>$ 40 mL/minute.
9. Expected survival $>$ 3 months
10. Voluntary written informed consent must be given before performance of any study-related procedure not part of standard medical care, with the understanding that consent may be withdrawn by the patient at any time without prejudice to future medical care.

5.2 Exclusion Criteria

Patients meeting any of the following exclusion criteria are not to be enrolled in the study.

1. Female patient who are both lactating and breast-feeding or have a positive serum pregnancy test during the screening period or a positive pregnancy test on Day 1 before first dose of study drug
2. Any serious medical or psychiatric illness that could, in the investigator's opinion, potentially interfere with the completion of treatment according to the protocol.
3. Known cerebral or meningeal disease (EBV- and CD30-positive lymphoma or any other etiology), including signs or symptoms of PML
4. Symptomatic neurologic disease compromising normal activities of daily living or requiring medications
5. Any sensory or motor peripheral neuropathy greater than or equal to Grade 2
6. Known history of any of the following cardiovascular conditions
 - a. Myocardial infarction within 1 year of study enrollment
 - b. New York Heart Association (NYHA) Class III or IV heart failure (see Appendix 12.2)
 - c. Evidence of current uncontrolled cardiovascular conditions, including cardiac arrhythmias, congestive heart failure (CHF), angina, or electrocardiographic evidence of acute ischemia or active conduction system abnormalities
 - d. Recent evidence (within 6 months before first dose of study drug) of a left-ventricular ejection fraction <50%
7. Any active systemic viral, bacterial, or fungal infection requiring systemic antibiotics within 2 weeks prior to first study drug dose
8. Patients that have not completed any prior treatment chemotherapy and/or other investigational agents within at least 5 half-lives of last dose of that prior treatment
9. Known hypersensitivity to recombinant proteins, murine proteins, or to any excipient contained in the drug formulation of brentuximab vedotin.
10. Known human immunodeficiency virus (HIV) positive
11. Known hepatitis B surface antigen-positive, or known or suspected active hepatitis C infection
12. Diagnosed or treated for another malignancy within 3 years before the first dose or previously diagnosed with another malignancy and have evidence of residual disease. Patients with nonmelanoma skin cancer or carcinoma in situ of any type are not excluded if they have undergone complete resection.

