6. Known history of myocardial infarction within 1 year, NYHA class III/IV heart failure, or uncontrolled cardiovascular conditions including cardiac arrhythmias, congestive heart failure (CHF), angina, or electrocardiographic evidence of acute ischemia or active conduction system abnormalities. Recent evidence (within 6 months before first dose of study drug) of a left-ventricular ejection fraction <50%.
7. Any active systemic viral, bacterial, or fungal infection within 2 weeks prior to first study drug dose
8. Any prior chemotherapy and/or other investigational agents within at least 5 half-lives of last dose
9. Prior stem cell transplantation within 100 days or radioimmunotherapy within 8 weeks
10. Prior exposure to CD30-targeted agents
11. Known hypersensitivity to recombinant proteins, murine proteins, or to any excipient contained in the drug formulation of brentuximab vedotin
12. Known human immunodeficiency virus (HIV) positive
13. Known hepatitis B surface antigen-positive, or known or suspected active hepatitis C infection
14. Another malignancy within 3 years before the first dose or previously diagnosed with another malignancy and have evidence of residual disease. Patients with nonmelanoma skin cancer or carcinoma in situ of any type are not excluded if they have undergone complete resection.

Duration of Study: This study will last approximately 30 months to reach the final analyses of the ORR and PFS (24 months of enrollment plus 6 months of additional follow-up after the last patient-in).

STUDY OVERVIEW DIAGRAM

SCHEDULE OF EVENTS

Timetables: screening ~ end of treatment

	Screening	Cycle 1	Cycle 2	Cycles 3~15	Cycle 16	EOT/EOS	FU ^a
	-28 to D1	D1	D1	D1	D1	30 ± 7 after last IP dose	q 3 mo till study closure
Visit window, days		± 3	± 3	± 3	± 3		
Informed consent	X						
Inclusion/exclusion	X						
Demographics	X						
Medical history	X						
Tumor specimen and biomarker sample	X ^b						
Height	X						
Weight	X	X	X	X	X		
Physical exam	X	X ^c	X	X	X	X	X
Serum β-hCG	X ^d						
Urine pregnancy test		X					
Vital signs	X	X ^e	X	X	X	X	X
ECOG performance status	X		X	X	X		
B symptoms	X	X	X	X	X	X	X
Hematology and chemistry ^f	X	X	X	X	X	X	X
12-lead ECG	X						
Concomitant medication	Concomitant medications and procedures will be recorded from signing the main ICF through 30 days after the last dose of brentuximab vedotin.						
AE reporting		Recorded from first dose of study drugs through 30 days after the last dose of brentuximab vedotin.					

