SAEs	SAEs will be collected from signing of the main ICF through 30 days after the last dose of brentuximab vedotin.						
CTs of the neck, abdomen, and pelvis ^g	X		X	X		X	
Skin evaluation ^h	X		X	X		X	
PET/CT ⁱ	X		X				
Survival and disease status							X ^j

- a. All treated patients will be followed for PFS and OS status every 12 weeks (\pm 1 week) until the study closure. For patients who have progressive disease, survival/disease status and information regarding the initiation of an alternative lymphoma treatment may be obtained by phone call.
- b. Tumor tissue at any time will be collected (five unstained slides at 4 μ m thickness or a paraffin-embedded block) after the patient has signed the screening ICF. This will be used to assess CD30 status using Ber-H2 antibody (DAKO, Glostrup, Denmark) and biomarkers associated with sensitivity or resistance to brentuximab vedotin (eg, beta3- tubulin etc). Biomarker samples will be collected (EDTA 5mL x1 plus SST 3mL x1) to assess lymphocyte subsets and soluble CD30 quantification.
- c. The Cycle 1 Day 1 physical exam is not required if the screening physical examination was conducted within 7 days before administration of the first dose of brentuximab vedotin. A limited physical exam may be administered at the treating physician's discretion.
- d. A serum β -hCG pregnancy test will be performed for women of childbearing potential during screening. A negative urine pregnancy test is required if the serum pregnancy test was not done within 7 days of the first dose of study drug.
- e. Vital signs should be measured at screening and within 1 hour prior to infusion of brentuximab at day 1 of each cycle and EOT.
- f. A blood sample for hematology and serum chemistry including LDH will be obtained at screening and pre-dose at day 1 of each cycle and EOT. Hematology and chemistry blood samples for cycle 1, day 1 may be collected within 7 days prior to dosing to ensure patient eligibility on study day 1.
- g. Response to treatment and disease status assessments will be evaluated according to the Revised Response Criteria for Malignant Lymphomas¹ and the modified SWAT criteria.² MRI scans may be substituted for CT scans only if a patient 1) has a glomerular filtration rate of less than 60 mL/min such that IV contrast presents a risk of renal failure, 2) develops anaphylaxis to IV contrast, or 3) becomes pregnant during long-term follow-up. If use of MRI is required, a consistent scanning modality must be maintained.

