4 STUDY DESIGN

4.1 Overview of Study Design

This is an open-label, non-randomized, multi-center, phase II trial of brentuximab vedotin to evaluate ORR primarily in patients with EBV- and CD30-positive lymphomas. The ORR will be evaluated based on the revised Cheson's criteria¹ or modified SWAT criteria² in case of cutaneous EBV- and CD30-positive lymphomas. Patients may receive up to 16 cycles of brentuximab vedotin.

Tumor measurements will be assessed (CT and PET scans) at screening, after completion of cycle 2 (Cycle 2 Day 21 ± 7 day), and at 4 to 8 weeks after the last dose of brentuximab vedotin. CT scans only will be used for the disease assessment follow-up every 3 months until the study closure.

Safety will be evaluated according to National Cancer Institute Common Terminology Criteria for Adverse Events (NCI CTCAE), Version 4.03, as well as by measuring changes from baseline in the patient's vital signs, ECOG performance status, electrocardiogram (ECG), and clinical laboratory results.

Patients may discontinue therapy at any time. Patients will attend the EOT visit 30 (± 7) days after completion of their last dose of brentuximab vedotin.

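### Nothing requires the baseline tumour assessment to follow the last prior treatment, and radiotherapy has no interval, so residual effect of earlier treatment could be scored as response

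*Combined protocol and SAP*

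**What the plan says.** **Baseline timing.** In the Schedule of Events the row "CTs of the neck, abdomen, and pelvis", the skin evaluation and PET/CT are all marked in the Screening column, which runs from Day -28 to Day 1. No shorter window is set for imaging. Section 4.1 adds only that "Tumor measurements will be assessed (CT and PET scans) at screening". Neither place relates the scan to the end of earlier treatment.

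**Washout.** Synopsis exclusion 8 reads "Any prior chemotherapy and/or other investigational agents within at least 5 half-lives of last dose". Section 5.2 item 8 reads "Patients that have not completed any prior treatment chemotherapy and/or other investigational agents within at least 5 half-lives of last dose". Both count in half-lives of the earlier agent, give no minimum in days, and do not say whether the interval runs to the scan, enrolment or first dose.

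**Radiotherapy and transplant.** Synopsis exclusion 9 bars "Prior stem cell transplantation within 100 days or radioimmunotherapy within 8 weeks". Section 5.2 has no such item. Neither list mentions external-beam radiotherapy.

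**Disease status.** Section 5.1 item 2c requires "Relapsed or refractory disease that fails to at least one and maximum four regimens including anthracycline-based chemotherapy", and item 4 requires "At least one measurable lesion based on revised Cheson's or modified SWAT criteria". Neither asks for progression after the most recent treatment, and neither restricts previously irradiated lesions. Appendices 12.3 and 12.4 have no rule for them either.

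**The concern.** Response is judged by change from baseline. In Appendix 12.3 a partial remission needs at least a 50% fall in the sum of the products of the diameters. If the baseline was taken before the last prior dose or fraction, or if the measured lesion was irradiated shortly before, part of that fall may belong to the earlier treatment.

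ORR is the primary endpoint, there is one arm, and Section 7.1.1 tests against a fixed 20%. No control group would share the carry-over, so it pushes toward passing stage 1 and toward a false positive at the end. The decision turns on 7 against 8 responders in 22, so one or two misattributed responses can settle it.

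**Working it through.** **1. The plan's own design.** Inputs from Section 7.1.1: p0 = 0.20, p1 = 0.45, continue if at least 3 of 10 respond, reject the null if at least 8 of 22 respond. The exact rejection probability is

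R(p) = sum over x = 3 to 10 of P(X1 = x) × P(X2 ≥ 8 − x), with X1 ~ Bin(10, p) and X2 ~ Bin(12, p).

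At p = 0.20 the terms are 0.0146 (x = 3), 0.0181 (x = 4), 0.0117 (x = 5), 0.0040 (x = 6), 0.0007 (x = 7) and less than 0.0001 each beyond that. They sum to R(0.20) = 0.0492. R(0.45) = 0.806. The stated 0.05 and 80% power are met, so the sample size is not in question.

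**2. Can the baseline precede the last prior dose?** Assume that the washout runs to first dose. For a prior agent with half-life h days it lasts 5h days. A scan 28 days before first dose then precedes the last prior dose whenever 5h < 28, that is h < 28/5 = 5.6 days. The largest gap is 28 − 5h. The documents give no half-lives for prior agents, so these values are assumed:

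| Half-life h (days) | Washout 5h (days) | Scan may precede last prior dose by (days) |
|---|---|---|
| 1 | 5 | 23 |
| 2 | 10 | 18 |
| 4 | 20 | 8 |

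For external-beam radiotherapy no interval is set, so fractions could fall anywhere between the scan and Day 1.

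**3. Illustrative effect on the test.** Suppose that the drug is inactive, with a true rate of 20%. Let a fraction f of patients be affected, and let q be their probability of being scored a responder. Then p = 0.20(1 − f) + qf. Both f and q are assumptions.

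| f | q | p | Chance of passing stage 1 | Type I error R(p) |
|---|---|---|---|---|
| 0 | – | 0.200 | 0.322 | 0.049 |
| 5% | 20% | 0.200 | 0.322 | 0.049 |
| 2% | 30% | 0.202 | 0.328 | 0.052 |
| 5% | 30% | 0.205 | 0.337 | 0.056 |
| 5% | 40% | 0.210 | 0.353 | 0.063 |
| 10% | 50% | 0.230 | 0.414 | 0.098 |
| 15% | 60% | 0.260 | 0.504 | 0.170 |

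Worked line: f = 10%, q = 50% gives p = 0.20 × 0.90 + 0.50 × 0.10 = 0.18 + 0.05 = 0.23, and R(0.23) = 0.098.

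**The case against.** The strongest reply is that the route is narrow. Patients must already have failed one to four regimens, and a failed regimen is an unlikely source of a 50% reduction. Any further regimen would count towards the cap of four. Section 5.1 item 6 also requires neutrophils of at least 1,500/μL and platelets of at least 75,000/μL (1,000 and 50,000 with marrow involvement). Footnote f of the Schedule allows the Cycle 1 Day 1 bloods to be drawn within 7 days before dosing to ensure eligibility on that day. In practice, count recovery limits dosing soon after myelosuppressive chemotherapy. The plan nowhere provides for treatment between scan and Day 1; that possibility comes from silence.

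Most of this stands for chemotherapy. It does not cover focal radiotherapy or agents that spare the marrow, and it does not make the scan follow the last treatment. Radiotherapy is also foreseeable here, since the PFS definition in Section 7.1.6 names it as a subsequent treatment.

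Three stronger readings are tempting and are not supported:

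- **Radiation in any form is unrestricted.** Synopsis exclusion 9 does cover radioimmunotherapy (8 weeks) and transplant (100 days). The gap is external-beam radiotherapy, plus the absence of that item from Section 5.2.
- **Section 5.2 item 8 deliberately reverses the washout.** Its literal wording does run against synopsis item 8, but this is best seen as a drafting defect. It needs reconciling and adds no evidence of bias.
- **The type I error is at least 0.063.** No document supports any particular f or q. A q of 40 to 60% gives affected patients two to three times the null rate, close to or above the 45% target for study drug. At q = 20% the error does not move.

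**Conclusion.** The point holds as a gap in eligibility and baseline timing. The rules as written allow a baseline taken before the last prior treatment and allow a recently irradiated lesion to be the sole measurable lesion. Either could turn residual effect into a scored response in an uncontrolled comparison.

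The chemotherapy route is unlikely, for the reasons given above. Radiotherapy, and any treatment given between the scan and Day 1, are the main open routes. The size cannot be derived from the documents: 0.049 to 0.056 for f of 2 to 5% with q of 20 to 30%, and up to 0.17 at 15% and 60%, are illustrations on assumed inputs. The 2/10, 7/22 design itself is correct and needs no change. The correction is worth making because it is cheap and protects the primary endpoint.

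**What to change.** - In the Schedule of Events and Section 5.1 item 4, state that the baseline CT, PET and mSWAT used for response must be obtained after the last dose or fraction of any prior anti-lymphoma treatment; if they were taken earlier, repeat them before Cycle 1 Day 1.
- State that a previously irradiated lesion counts as measurable for response only if growth since irradiation is documented.
- Reconcile Section 5.2 item 8 with synopsis item 8, including the date to which the interval runs, and reconcile Section 5.2 with synopsis item 9. The length of any washout, including whether to set one for radiotherapy, is for the sponsor to decide.

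The cost is protocol wording, re-timing of some screening scans and, rarely, a repeat scan. Sample size and decision rules stay as they are.

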6 STUDY DRUG

6.1 Brentuximab Vedotin Administration

Study drug will be administered only to eligible patients under the supervision of the investigator or identified subinvestigator(s).

Brentuximab vedotin must not be administered as an IV push or bolus. Study treatment will be administered by IV infusion given over approximately 30 minutes on Day 1 of each 21-day cycle. In the absence of infusion toxicities, the infusion rate for all patients must be calculated in order to achieve a 30-minute (approximate) infusion period. Brentuximab vedotin will be administered through a dedicated IV line and cannot be mixed with other medications.

The dose of brentuximab vedotin is 1.8 mg/kg. Dosing is based on patients' weight according to the institutional standard; however, doses will be adjusted for patients who experience a $\geq 10\%$ change in weight from baseline. Actual weight will be used except for patients weighing greater than 100 kg; dose will be calculated based on 100 kg for these individuals. The dose will be rounded to the nearest whole number of milligrams.

Infusion-related reactions may occur during the infusion of brentuximab vedotin. The infusion should be administered at a site properly equipped and staffed to manage anaphylaxis should it occur. The patient should be observed for 60 minutes following the first infusion of brentuximab vedotin.

During this observation period, the IV line should remain open for at least 1 hour to allow administration of IV drugs if necessary. All supportive measures consistent with optimal patient care will be given throughout the study according to institutional standards. Medications for infusion-related reactions, such as epinephrine, antihistamines, and corticosteroids, should be available for immediate use.

Patients who experience a Grade 1 or Grade 2 infusion-related reaction may receive subsequent brentuximab infusions with premedication consisting of acetaminophen (650 mg orally) and diphenhydramine (25–50 mg orally or 10–25 mg IV) or according to institutional standards, administered 30 to 60 minutes prior to each 30-minute brentuximab vedotin infusion. The routine use of steroids as premedication is discouraged.

If a Grade 3 or greater infusion-related reaction consistent with anaphylaxis occurs, immediately and permanently discontinue administration of brentuximab vedotin and administer appropriate medical therapy as per institutional guidelines.

6.2 Dose Modification Guidelines

Brentuximab vedotin dose modifications may change depending on the disease and combination with other drug(s).

Table 6-1 and Table 6-2 detail the recommended brentuximab vedotin dose modifications to be enacted in the event of treatment-associated toxicity.

Table 6-1 Recommended brentuximab vedotin Dose Modifications for Treatment-Associated Toxicity Excluding Neuropathy

Toxicity	≤Grade 2	Grade 3	Grade 4
Non-hematologic (excluding neuropathy)	Continue at same dose level.	Withhold dose until toxicity is ≤ Grade 1 or baseline, then resume treatment at the same dose and schedule ^a .	Withhold dose until toxicity is ≤ Grade 1 or has returned to baseline, then reduce dose to 1.2 mg/kg and resume treatment, or discontinue at the discretion of the investigator. ^a
Hematologic	Continue at same dose level.	Withhold dose until toxicity is ≤ Grade 2, or baseline, then resume treatment at the same dose level ^b . Consider growth factor support (G-CSF or GM-CSF) in subsequent cycles. ^b	Withhold dose until toxicity is ≤ Grade 2 or baseline, then resume treatment at the same dose and schedule. Consider growth factor support (G-CSF or GM-CSF) in subsequent cycles for patients who develop Grade 3 or Grade 4 neutropenia. ^b

NOTE: Grading based on National Cancer Institute (NCI) Common Terminology Criteria for Adverse Events (CTCAE) v. 4.03

- a Patients who develop Grade 3 or 4 electrolyte laboratory abnormalities may continue study treatment without interruption. Brentuximab vedotin will be held for clinically meaningful Grade 3 or 4 electrolyte abnormalities.
- b Patients who develop Grade 3 or 4 lymphopenia may continue study treatment without interruption.

Table 6-2 Dosing Recommendations for Treatment-Emergent or Worsening Peripheral Sensory or Motor Neuropathy

Severity of Peripheral Sensory or Motor Neuropathy (Signs and Symptoms [abbreviated description of CTCAE])	Modification of Dose and Schedule
Grade 1 (Asymptomatic; clinical or diagnostic observations only; intervention not indicated; paresthesia and/or loss of deep tendon reflexes)	Continue with the same dose and schedule
Grade 2 (Moderate symptoms; limiting instrumental activities of daily living)	Withhold dose until toxicity returns to \leq Grade 1 or baseline, then restart treatment at a reduced dose of 1.2 mg/kg every 3 weeks
Grade 3 (Severe symptoms; limiting self care activities of daily living)	
Grade 4 (life-threatening consequences; urgent intervention indicated)	Discontinue treatment
Grade 5 (Death)	

NOTE: Grading based on National Cancer Institute (NCI) Common Terminology Criteria for Adverse Events (CTCAE) v. 4.03; see neuropathy; peripheral motor neuropathy; peripheral sensory neuropathy.

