Although infections were observed in 61% of patients in the completed phase 2 studies (Studies SG035-0003 and SG035-0004), the majority of infections were Grade 1 to 2 and occurred with an incidence comparable to that reported in similar populations. While serious infections were reported in 10% of patients, the majority of infections were not considered by the investigator to be related to brentuximab vedotin. Infection led to dose delay in 14% of HL patients and 7% of ALCL patients. No patient discontinued treatment because of infection. The infection with the highest incidence was Grade 1 or 2 URTI, which occurred in more HL than ALCL patients. Grade 3 or 4 infections occurred in 7% of HL patients and 12% of ALCL patients. No Grade 5 infections were reported. HL patients had a higher incidence of infections, largely reflective of the higher incidence of Grade 1 to 2 URTI (37%). Several factors may have contributed to this higher incidence, including the high frequency of respiratory tract infections in HL patients post-transplant, the lower median age of the HL patients compared with systemic ALCL patients, and differences in exposure to respiratory viruses. These URTIs, while frequent, led to dose delay in only 3 patients. Importantly, the rate of pneumonia was low, which is indicative of a low rate of progression from URTI to pneumonia, and the incidence was lower than that reported in the literature for comparable populations.

Stevens-Johnson Syndrome

Stevens-Johnson syndrome and toxic epidermal necrolysis have been reported with brentuximab vedotin. Fatal outcomes have been reported. If Stevens-Johnson syndrome or toxic epidermal necrolysis occur, brentuximab vedotin must be discontinued and the appropriate medical therapy administered.

Tumor Lysis Syndrome

Tumor lysis syndrome (TLS) is typically reported in patients with acute leukemias and high-grade non-Hodgkin lymphomas after the initiation of cytotoxic therapy.

TLS has been reported with brentuximab vedotin. Patients with rapidly proliferating tumor and high tumor burden are at risk of tumor lysis syndrome. These patients should be monitored closely and managed according to best medical practice. Management of TLS may include aggressive hydration, monitoring of renal function, correction of electrolyte abnormalities, anti-hyperuricaemic therapy, and supportive care.

Progressive Multifocal Leukoencephalopathy

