PML can occur in patients receiving brentuximab vedotin. PML is a rare demyelinating disease of the brain that is caused by the John Cunningham virus (JCV). It typically occurs in immunocompromised individuals and can be fatal. Presenting features may include altered mental status, motor deficits such as hemiparesis or ataxia, visual disturbances, or higher cortical dysfunction such as dysphasia or agnosia. Seizures have also been reported in PML patients (approximately 20%). The onset of neurological deficits may occur over weeks to months.

Cognitive decline without accompanying deficits in motor or sensory function is uncommon. Optic nerve involvement, fever, and spinal cord disease are not typically associated with PML. In addition, peripheral neuropathy, which has been reported with brentuximab vedotin treatment, is not commonly reported with PML.

If PML is suspected, a diagnostic work-up should be performed. The work-up may include, but is not limited to:

- Neurologic examinations, as warranted
- Brain MRI: features suggestive of PML include presence of unifocal or multifocal lesions, mainly of the white matter, which are typically non-enhancing and do not have mass effect.
- PCR analysis: JCV DNA detectable in CSF or there is evidence of JCV in a brain biopsy
- Neurology consultation

Brentuximab vedotin dosing should be held if PML is suspected. If PML is confirmed, brentuximab vedotin should be permanently discontinued.

Pulmonary Toxicity in Combination with Bleomycin

Concomitant use of brentuximab vedotin and bleomycin is contraindicated due to pulmonary toxicity. In a clinical trial that studied brentuximab vedotin with bleomycin as part of a combination regimen (ABVD), the rate of noninfectious pulmonary toxicity was higher than the

historical incidence reported with ABVD. Monotherapy with brentuximab vedotin has not been associated with a clinically meaningful risk of pulmonary toxicity. In the event of new or worsening pulmonary symptoms (e.g., cough, dyspnoea), a prompt diagnostic evaluation should be performed and patients should be treated appropriately.

Acute Pancreatitis

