Acute pancreatitis has been reported for patients treated with brentuximab vedotin. Patients should be monitored for signs of new or worsening acute abdominal pain and, if observed, a diagnostic workup for pancreatitis should be considered. A diagnostic workup may include physical examination, laboratory evaluation for serum amylase and serum lipase, and abdominal imaging, such as ultrasound and other appropriate diagnostic measures. Brentuximab vedotin should be held for any suspected case of acute pancreatitis. Brentuximab vedotin should be discontinued if a diagnosis of acute pancreatitis is confirmed.

Hepatotoxicity

Hepatotoxicity, predominately in the form of asymptomatic mild to moderate transient elevations in AST and/or ALT, has been reported for patients treated with brentuximab vedotin. Patients should be monitored for elevated liver enzymes.

Embryogenesis, Reproduction, and Spermatogenesis

The effects of brentuximab vedotin on embryogenesis, reproduction, and spermatogenesis in humans are unknown. In addition, data about the effects of brentuximab vedotin in pregnant women are unavailable. Therefore, women of childbearing potential and fertile men should be advised to use adequate and effective contraception during and after treatment with brentuximab vedotin.

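### Table 6-1's Grade 3 and Grade 4 rules contradict the discontinuation rules in sections 6.1 and 6.6 for anaphylaxis, SJS/TEN, confirmed PML and confirmed acute pancreatitis

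*Combined protocol and SAP*

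**What the plan says.** Section 6.2 states that Tables 6-1 and 6-2 "detail the recommended brentuximab vedotin dose modifications to be enacted in the event of treatment-associated toxicity". The title of Table 6-1 gives its scope as "Dose Modifications for Treatment-Associated Toxicity Excluding Neuropathy", and the label of the non-hematologic row repeats that single exclusion. The row has three cells:

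- Grade 2 or lower: carry on at the same dose.
- Grade 3: withhold until the toxicity is back to Grade 1 or baseline, then restart with dose and schedule unchanged. Stopping is not offered.
- Grade 4: withhold to the same point, "then reduce dose to 1.2 mg/kg and resume treatment, or discontinue at the discretion of the investigator".

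Footnote a deals with electrolyte abnormalities and footnote b with lymphopenia. Neither names any other event.

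Four events have their own instructions elsewhere:

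- Anaphylaxis, section 6.1: "If a Grade 3 or greater infusion-related reaction consistent with anaphylaxis occurs, immediately and permanently discontinue administration of brentuximab vedotin". Section 6.6 (Infusion-Related Reactions) and section 1.6 give the same consequence for anaphylaxis without a grade limit.
- SJS/TEN, section 6.6: "If Stevens-Johnson syndrome or toxic epidermal necrolysis occur, brentuximab vedotin must be discontinued". Section 1.6 repeats this.
- PML, section 6.6: dosing is held on suspicion, and then "If PML is confirmed, brentuximab vedotin should be permanently discontinued".
- Acute pancreatitis, section 6.6: dosing is held on suspicion, and "Brentuximab vedotin should be discontinued if a diagnosis of acute pancreatitis is confirmed".

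**The concern.** All four events are non-hematologic and none is neuropathy, so on its wording the table covers them. A site that doses from the table can therefore reach a different action from a site that works from sections 6.1 and 6.6, and nothing in section 6.2 tells either site which text to follow.

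What is at stake is re-exposure of a patient. The protocol reports fatal cases of PML (section 1.4), acute pancreatitis (sections 1.4 and 1.6) and SJS/TEN (sections 1.6 and 6.6). It also says in section 6.6 that hypersensitivity reactions to infused proteins may be fatal if poorly managed. The trial is multi-center and the Protocol Summary states that no independent data monitoring committee is planned, so consistent handling depends largely on the written rule.

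**Working it through.** No sample size, power or error rate enters this point. The check sets the texts side by side, then looks for anything that resolves the difference.

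**1. Cell against event rule**

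| Grade | Table 6-1, non-hematologic row | Sections 6.1 and 6.6, four events | Result |
|---|---|---|---|
| 3 | Withhold, then restart unchanged; no option to stop | Discontinue (PML and pancreatitis: once confirmed); no restart | Direct conflict |
| 4 | Withhold, then restart reduced, or stop at discretion | As above | Conflict if the site restarts; none if it stops |
| 2 or lower | Carry on | Section 6.6 sets no grade threshold; hold on suspected PML or pancreatitis | Cannot be settled from the documents |

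At Grades 3 and 4 the table's instruction to withhold agrees with the hold for suspected PML or pancreatitis. The texts part once the diagnosis is confirmed.

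The last row depends on which CTCAE grades each event can take. Appendix 12.1 gives only a web link, so I draw no conclusion there.

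**2. Strength of the wording**

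The event rules differ in force. SJS/TEN uses *must*, section 6.1 uses an imperative for anaphylaxis, and the section 6.6 rules for anaphylaxis, PML and pancreatitis use *should*. Permanence is stated for anaphylaxis and PML but not for SJS/TEN or pancreatitis. None of the four rules provides for restarting.

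**3. Is there a precedence rule or a cross-reference?**

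- Section 6.2 refers to neither 6.1 nor 6.6.
- Section 6.6 refers back to 6.2 only in the neutropenia paragraph.
- Section 6.12 gives the investigator a right to withdraw a patient for an adverse event, but lists no event that ends treatment.
- Section 1.6 sends the reader to Section 5.2 for dose modification and to Section 5.6 for management of clinical events. Section 5.2 is the exclusion criteria and there is no 5.6; the intended places are 6.2 and 6.6.

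**4. The two anaphylaxis triggers**

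Section 6.1 acts on a reaction of Grade 3 or greater that is consistent with anaphylaxis. Section 6.6 acts on any anaphylaxis. These also differ from each other.

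**5. How often it could arise**

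Section 1.4 puts acute pancreatitis at no more than 0.5%. With 25 treated patients, and assuming that this figure carries over to them:

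- Expected cases: 25 × 0.005 = 0.125 at most.
- Chance of at least one: 1 − 0.995^25 ≈ 0.12 at most.

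The documents give no incidence for anaphylaxis, SJS/TEN or PML on this drug, so no figure is offered for them.

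**The case against.** The strongest reply is that a specific instruction governs over a general one. Table 6-1 is a generic grade grid, described as recommended and placed under guidelines. The four events have their own text, in places repeated: anaphylaxis in sections 1.6, 6.1 and 6.6, SJS/TEN in 1.6 and 6.6. Nothing outside the table tells a site to rechallenge. Section 6.12 also lets an investigator stop for any adverse event, so the table does not force re-exposure.

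That reading is plausible, and a careful investigator would probably adopt it. But the protocol never states it, and two features cut against it. Section 6.2 says that its modifications are to be enacted, and its authors wrote exceptions where they wanted them (neuropathy, electrolytes, lymphopenia). In addition, the neuropathy and neutropenia paragraphs of section 6.6 defer to what individual protocols specify, which could lead a reader to take 6.6 as background guidance and the table as this trial's operative rule.

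Parts of the reply do stand. A site that stops treatment at Grade 4 complies with both texts, so that cell is not a flat opposite. A reader might also infer that the lowest-grade cell tells sites to carry on through confirmed PML or pancreatitis; without the CTCAE grades the documents do not show this. Nor do they support the inference that safety results become non-comparable between centers: no between-center comparison is planned, and section 7.1.8 only tabulates reasons for discontinuation.

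**Conclusion.** The contradiction holds for Grade 3 and, where the site chooses to restart, for Grade 4. It covers four events: anaphylaxis, SJS/TEN, confirmed PML and confirmed acute pancreatitis. The Grade 3 cell is the clearest case because it leaves no room for stopping. It is an error in the text as written and should be corrected on patient-safety grounds, although the number of patients affected may be small or zero. It has no bearing on the two-stage design or the error rates of the response-rate test.

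The conclusion rests on reading the table's scope literally and on the absence of any precedence statement. Two stronger readings should not be drawn. The first is that discontinuation is mandatory and permanent for all four events: the wording for pancreatitis and PML is conditional on confirmation and uses *should*. The second is that fewer than one case of each event can be expected: the documents support that for pancreatitis only.

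**What to change.** Reconcile Table 6-1 with sections 6.1 and 6.6 so that one instruction applies to each of the four events. One way is a footnote to the non-hematologic row that names anaphylaxis, SJS/TEN, acute pancreatitis and PML, and states which section governs them and that it takes precedence over the grade columns. The footnote should name anaphylaxis and not infusion-related reactions in general, because section 6.1 has separate provisions for Grade 1 and 2 reactions that do not conflict with the table.

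In the same amendment, reconcile the two anaphylaxis triggers (section 6.1 with a grade limit, section 6.6 without) and correct the section numbers cited in section 1.6.

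Which clinical rule applies to each event is for the sponsor-investigator to decide; this point takes no view on it. The cost is one footnote, the reconciled anaphylaxis wording and corrected cross-references, with no added patients, visits or procedures.
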